6.2.2 Exclusion Criteria

Any of the following conditions are cause for exclusion from the study:

1. Patients posing a serious suicidal risk and/or in need of immediate hospitalization as judged by the Investigator;
2. Patients with a diagnosis of Bipolar I or II disorder;
3. Patients with a current Axis I diagnosis of:
 - Delirium
 - Dementia
 - Amnestic and/or other cognitive disorder
 - Schizophrenia or other psychotic disorder;
4. Patients having experienced hallucinations, delusions, or any psychotic symptomatology within the current depressive episode or during prior depressive episodes;
5. Patient is currently in an inpatient facility;
6. Patients with a history of hypothyroidism unless taking a stable dose of thyroid medication and asymptomatic or euthyroid for at least 6 months;

7. Patients who meet DSM-IV-TR criteria for any significant current substance use disorder;
8. Patients with:
 - hepatic insufficiency (three times the upper limit of normal (ULN) for aspartate aminotransferase (AST) and/or alanine aminotransferase (ALT)); liver transplant recipient; cirrhosis of the liver;
 - malignancy (except basal cell carcinoma) and/or chemotherapy within 1 year prior to screening; malignancy more than 1 year prior to screening must have been local and without metastasis and/or recurrence, and if treated with chemotherapy, without nervous system complications;
 - significant unstable medical condition or life threatening disease with anticipated survival of less than 6 months;
 - need for therapies that may obscure the results of treatment and/or of the study;
9. Participation in another clinical trial within 30 days of the screening visit;
10. Anticipated inability to attend scheduled study visits;
11. Patients who in the judgment of the Investigator may be unreliable or uncooperative with the evaluation procedure outlined in this protocol;
12. Patients with a history of prior pharmacogenomic testing;
13. Any change in psychotropic medication (including change in dosage) between screening and baseline;
14. Patients currently receiving electroconvulsive therapy (ECT), deep brain stimulation (DBS) or transcranial magnetic stimulation (TMS) treatments, or currently scheduled to receive maintenance treatments of ECT, DBS, or TMS during the course of the study;
15. Patients who self-report to be pregnant or lactating;
16. Patients with a history of gastric bypass surgery

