7.1.3 Treatment as Usual (TAU)

Patients randomized to the TAU arm will also have their DNA collected and a pharmacogenomics-based interpretive report will be generated using GEN testing. However, this report will not be shared with the treating clinicians until up to 28 days prior to the completion at 12 months of the study at which point the report will be provided to

the participant by the treating clinician. Therefore, patients in this arm will receive clinical treatment as usual, without the use or knowledge of genotyping results by their treating clinicians.

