8.2 Secondary Outcome Measures

8.2.1 Clinical Outcome Measures of MDD Symptoms and Medication Side Effects

i. 16-Item Self-Report Quick Inventory of Depressive Symptomatology (QIDS-SR16)

The QIDS-SR16 is a patient reported measure designed to assess the severity of depressive symptoms(17, 18). The scale assesses the nine DSM-IV criteria symptom domains for major depression: sad mood, concentration, self-outlook, suicidal ideation, involvement, energy/fatigability, sleep disturbance (4 items: initial, middle, late insomnia, and hypersomnia), appetite/weight increase/decrease (4 items), and psychomotor agitation/retardation (2 items) (see Appendix III).

ii. 9-Item Patient Health Questionnaire (PHQ-9)

The PHQ-9 consists of nine questions, rated 0–3 according to the increased frequency of difficulty experienced in each area covered. Scores are self-rated by patients, with a possible range of 0–27, are summed and can then be interpreted as follows: no depression (0), minimal (1–5), mild (6–9), moderate (10–14), moderately severe (15–19), or severe (>20) depression (see Appendix IV).

iii. Generalized Anxiety Disorder 7-Item (GAD-7) Scale

The GAD-7 is a brief measure of symptoms of anxiety, based on diagnostic criteria described in DSM-IV(19). It consists of seven questions and is calculated by assigning scores of 0, 1, 2, and 3, to the response categories of “not at all”, “several days”, “more than half the days,” and “nearly every day,” respectively (see Appendix V).

iv. Clinical Global Impression (CGI)

The Clinical Global Impression Scale (CGI) is a brief clinician-rated instrument that consists of three different global measures (see Appendix VI):

- Severity of illness: overall assessment of the current severity of the patient's symptoms (CGI-S);
- Global improvement: overall comparison of the patient's baseline condition with his current state (CGI-I);
- Efficacy index: overall comparison of the patient's baseline condition to a ratio of current therapeutic benefit and severity of side effects (CGI-EI).

v. Changes to initial prescribing based on availability of pharmacogenomic data

The influence of pharmacogenomic data on a physician's initial prescription for both GEN and E-GEN will be evaluated by documenting the psychotropic medication prescribed before the availability of the pharmacogenomics data. This will be compared to changes (if any) to the physician's prescription when pharmacogenomics data becomes available.

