9.2 Enrollment and Randomization

Patients who meet all the inclusion/exclusion criteria will be enrolled in the study with a 1:1:1 randomization allocation to one of three groups: GEN, E-GEN, or TAU. Investigators will be then given the results of the GEN test for the participants randomized to GEN, and of the E-GEN test for the participants randomized to E-GEN. Investigators will use the report to support their treatment decision based on this information. However, raters and participants will be blinded.

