16.1.5 Within-Group and Between-Group Composite Phenotype Analyses

A three-level indicator variable (eg., green, yellow, and red categories) will be created using a proprietary algorithm which combines the phenotypes ascribed to each gene for each participant and drug metabolism information for each of the GeneSight panel drugs. This is done to reduce the dimensionality inherent to such data by generating a single composite phenotype for each participant. The final indicator variable will be labeled 'composite_phenotype,' with the first level scored as 'green,' (e.g., use medication(s) as directed) the second level scored as 'yellow,' (e.g., use medication(s) with caution) and the third level scored as 'red' (e.g., use medication(s) with caution and frequent monitoring). If parametric assumptions are upheld, 1-way independent ANOVA models will be employed to test the independent ability of the composite phenotype variable to predict each respective continuous outcome (i.e., percent improvement from baseline for HAMD-17) between study groups. If parametric (i.e., standard) assumptions are not met, GEEs will be employed to test the independent ability of the composite phenotype variable to predict each respective continuous outcome. Three tests will be conducted for each

continuous outcome: an overall ANOVA test and two planned contrasts involving the comparison of the first level (i.e., green category) to that of the third (i.e., red category), and the first two levels (i.e., green and yellow categories) of the composite phenotype variable to that of the third level. To account for multiple testing, the Sidak correction will be employed using the formula $1 - (1-\alpha)^{1/n}$ where n is the number of independent tests and α is the nominal level (i.e., 05) of statistical significance

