### **5.2 Secondary & Exploratory Efficacy Analyses**

The secondary analyses will be conducted using MMRM method for continuous response variables and ANCOVA with robust regression for complete cases for the PP population and may also be conducted for the ITT population.

As a secondary analysis, the following covariates will be added to the primary endpoint model with baseline score and analyzed the same way: treatment, age, gender, site type, and race included in the model. If covariates are not statistically significant, they may be dropped from the final model.

The secondary and exploratory measures of efficacy including percentage change from baseline in HAM-D6, QIDS-SR16, PHQ-9, GAD-7, CGI-S, change in EuroQol (EQ-5D-5L), and change in SF-36 will be analyzed the same way as for the primary efficacy variable above with baseline score included in the model. The secondary measures of efficacy will also be analyzed with baseline score, treatment, gender, site type, age, and race included in the model. If covariates are not statistically significant, they may be dropped from the final model.

Percentage of responders for HAM-D17, HAM-D6, QIDS-SR16, PHQ-9, GAD-7, CGI-S, CGI-I, CGI-EI, and SF-36, and remitters for HAM-D17, HAM-D6, QIDS-SR16, PHQ-9, GAD-7, and CGI-S will be analyzed by visit, separately, using a Generalized Linear Mixed model. Pre-specified covariates may be added.

Percentage of patients on congruent and incongruent medications will be compared between GEN and TAU using Chi-square tests at each time point.

Medication compliance using BARS and prescription filling data will be summarized and compared between treatment groups (see 7.6 for description).

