### **7.4 Definition of Congruence**

Congruence relates to whether the physician follows the combinatorial pharmacogenetic test recommendations. A three-level indicator variable (eg., green, yellow, and red categories) will be created using a proprietary algorithm which combines the phenotypes ascribed to each gene for each participant and drug metabolism information for each of the GeneSight panel drugs. Medications were considered congruent with the combinatorial pharmacogenomic test results if they were classified in green ('use as directed') or yellow ('use with caution') report categories. Incongruent medications were classified as those in red ('use with increased caution and more frequent monitoring') report category.

Prescribing is considered congruent if a patient is prescribed only congruent medications. Prescribing was considered incongruent if a patient is prescribed one or more incongruent medications. Patients will be categorized as congruent or incongruent at baseline using prescribed medications reported at baseline and at Week 8 using prescribed medications reported at Week 8.

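### The exploratory congruence endpoint is tested by unadjusted chi-square although baseline congruence can be derived in both arms: a valid test that gives up power when baseline status predicts later status

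*SAP*

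**What the plan says.** **The test.** SAP 5.2 gives the whole analysis of this endpoint in one sentence: "Percentage of patients on congruent and incongruent medications will be compared between GEN and TAU using Chi-square tests at each time point". The permission in 5.2 to add pre-specified covariates belongs to the responder and remitter models in the paragraph before. SAP 2.1.4 lists the comparison among exploratory objectives, at Weeks 8 and 12 and Months 6, 9 and 12.

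**The baseline value.** SAP 7.4 says: "Patients will be categorized as congruent or incongruent at baseline using prescribed medications reported at baseline". A patient is congruent if every prescribed drug is green or yellow, and incongruent if at least one is red.

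**Availability in TAU.** Protocol 7.1.3: "Patients randomized to the TAU arm will also have their DNA collected and a pharmacogenomics-based interpretive report will be generated using GEN testing". The report is withheld from the clinician until close to Month 12, but the bins exist.

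**Use of the baseline value.** It is not among the covariates in SAP 3.3, nor in the models of 5.1 and 5.2. Protocol 16.1.5 planned to relate the colour category to HAM-D17 improvement, to "test the independent ability of the composite phenotype variable to predict each respective continuous outcome". SAP 1.2 supersedes the protocol's analysis plan, and only the category definition carries over.

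**The concern.** Congruence is the SAP's measure of whether the report changed prescribing. A patient's drugs at Week 8 probably depend on the drugs at entry: a patient on a red-bin drug may well still be on it, and one on green or yellow drugs has less to change. The unadjusted test leaves that between-patient variation in the error term, although the variable that would remove it is already defined.

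The definition also has two loose ends. The Baseline visit (protocol 9.3) records both the current drugs and any change of prescription made in the light of the report, so drugs reported at baseline could mean either list. The SAP also does not say how to classify a patient who takes none of the 33 drugs in protocol Appendix I. Inclusion criterion 3 makes such patients possible, since it admits those who stopped a drug for intolerance.

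**Working it through.** **Inputs from the documents.** 190 per arm and 16.7% discontinuation by Week 8 (protocol 10.0): 190 × (1 − 0.167) = 158 per arm. Two-sided 0.05 (SAP 6). The documents state no power for congruence, so there is no planned figure to reproduce. The total of 570 sizes HAM-D17 and does not bear on this point.

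**Assumed inputs (not in the documents).** q = share incongruent at baseline. p = probability that such a patient is still incongruent at Week 8. c = probability that a baseline-congruent patient becomes incongruent. Subscripts T (TAU) and G (GEN).

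**Formulas.**
- Week 8 incongruence per arm: π = q·p + (1 − q)·c; Δ = π_T − π_G.
- Unadjusted variance: V_u = π_T(1 − π_T) + π_G(1 − π_G).
- Variance after standardising to baseline status: V_s = q[p_T(1 − p_T) + p_G(1 − p_G)] + (1 − q)[c_T(1 − c_T) + c_G(1 − c_G)] + q(1 − q)[(p_T − p_G) − (c_T − c_G)]².
- Chi-square power: Φ{[Δ − 1.96·√(2π̄(1 − π̄)/n)] / √(V_u/n)}, where π̄ is the mean of π_T and π_G.
- Stratified power: Φ{Δ/√(V_s/n) − 1.96}.

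**Case A: q = 0.25, p = 0.75 vs 0.50, c = 0.06 vs 0.04.**
- π_T = 0.1875 + 0.045 = 0.2325; π_G = 0.125 + 0.03 = 0.155; Δ = 0.0775.
- V_u = 0.1784 + 0.1310 = 0.3094.
- V_s = 0.1094 + 0.0711 + 0.1875 × 0.23² = 0.1904; ratio 0.62.
- Chi-square: (0.0775 − 0.0872)/0.0443 = −0.22, power 41%. Stratified: 0.0775/0.0347 − 1.96 = 0.27, power 61%.

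**Case B: q = 0.25, p = 0.50 vs 0.20, c = 0.15 vs 0.08.**
- π_T = 0.125 + 0.1125 = 0.2375; π_G = 0.05 + 0.06 = 0.11; Δ = 0.1275.
- V_u = 0.1811 + 0.0979 = 0.2790.
- V_s = 0.1025 + 0.1508 + 0.1875 × 0.23² = 0.2632; ratio 0.94.
- Chi-square: (0.1275 − 0.0836)/0.0420 = 1.05, power 85%. Stratified: 0.1275/0.0408 − 1.96 = 1.16, power 88%.

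**Simulated power, case A persistence and new-incongruence rates.**

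| Incongruent at baseline | Chi-square | Mantel-Haenszel |
|---|---|---|
| 15% | 29% | 42% |
| 25% | 41% | 61% |
| 35% | 54% | 76% |

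**Wider range.** A simulation of 20 scenarios (20,000 runs each) used q from 10% to 40%, p from 60–80% in TAU and 40–50% in GEN, and c from 5–10% in TAU and 2–5% in GEN. The stratified test gained in every one, by about 2 to 26 points. The largest gain was at q = 20%, p = 80% vs 50%, c = 5% vs 2%: 54% to 80%. When later status did not depend on baseline status (20% vs 10% in both strata), both tests had 71%. Type I error was about 0.05 for both.

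**Optional HAM-D17 interaction.** Assume d = 0.5 in the baseline-incongruent share q, no effect elsewhere, and 158 per arm. Then z = 0.5·√(158·q(1 − q)/2), which is 1.78, 2.04 and 2.22 at q = 0.2, 0.3 and 0.5. Power is 43%, 53% and 60%.

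**The case against.** The best defence is that nothing here is wrong. The chi-square compares randomised groups and holds its error rate. The endpoint is exploratory with no power claimed, and the gain depends on rates that nobody has stated. Case B shows that it can be small. All of that stands, and it limits this point to an efficiency gain.

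Three stronger readings are tempting and are not supported.

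- *Baseline congruence is contaminated by the report.* A reader might infer this because reports are normally released and viewed by the Baseline visit (SAP 3.2.1). But protocol 9.3 has the current drugs recorded before any antidepressant change, and exclusion criterion 13 bars "Any change in psychotropic medication (including change in dosage) between screening and baseline". Protocol 9.1 also forbids changes in that interval, except for benzodiazepines, which are not on the Appendix I panel. A clean value exists. What remains is an ambiguity in SAP 7.4 about which list is meant.
- *A null HAM-D17 result could not be interpreted.* SAP 4.1 summarises baseline variables, and the chi-square at each time point can be read to include baseline. Either would show whether most patients were already congruent. What is missing is the HAM-D17 effect by baseline congruence.
- *The report can act only in baseline-incongruent patients, so they alone should be analysed.* The report may also prevent a new red-bin prescription or guide choices among yellow-bin drugs (protocol 7.1.1). In one simulated scenario (q = 20%, p = 60% vs 40%, c = 10% vs 5%) restricting to that subset lowered power from 49% to 36%. Adjustment in the full sample is the safer form.

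**Conclusion.** The point holds as a free improvement. SAP 5.2 tests congruence without adjustment although a baseline value is defined and derivable in both arms. The test is valid. Its cost is power: about 2 to 26 points at 158 per arm over the assumed rates, and nothing if baseline status does not predict later status. Some dependence is likely for the same patient's drugs eight weeks apart, but its strength is not in the documents, so no single figure should be quoted as the loss. The primary HAM-D17 analysis is unaffected.

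**What to change.** 1. **SAP 5.2.** Replace the post-baseline chi-square with a Mantel-Haenszel or logistic comparison of GEN and TAU in the full sample, adjusted for baseline congruence. A descriptive baseline comparison can stay.
2. **SAP 7.4.** State that baseline congruence uses the current psychotropic drugs before the report could act (the Screening list, or the Baseline list recorded before any change), not the new prescription also recorded at Baseline. Protocol 8.2.1 already provides for "documenting the psychotropic medication prescribed before the availability of the pharmacogenomics data". Say how patients on no panel drug are classified. Extend the patient-level definition, now given only for baseline and Week 8, to the later visits in SAP 2.1.4.
3. **Optional.** Pre-specify one supportive, exploratory treatment-by-baseline-congruence analysis of Week 8 HAM-D17. State its limited power (about 43%, 53% and 60% under the assumptions above) and that the report may also affect baseline-congruent patients.

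The cost is SAP wording and, if item 3 is taken up, one extra model. No new data are collected. Item 2 should be settled before unblinding, because the handling of patients on no panel drug affects who enters the comparison.

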### **5.3 Safety and Tolerability Analysis**

Descriptive statistics for the number of AE's by treatment and week will be generated. The percentage of subjects who experienced AE's may be analyzed using a Generalized Linear Mixed model. The model would include treatment, gender, age, and baseline HAM-D17 score. Continuous measures including UKU, FIBSER, and weight gain may be analyzed in a similar manner as for the primary efficacy variable above.

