4.3 Secondary Objectives

To compare the three intervention alternatives (GEN, E-GEN, and TAU) with respect to:

- MDD symptoms;
- Changes to initial prescribing based on availability of pharmacogenomics data;
- Response rates to psychotropic medication;
- Remission rates;
- Time to response/remission;
- Medication side effects, including weight gain;
- Health-related quality of life;
- Physician's attitude and experience to DNA testing;
- Healthcare resource utilization and productivity losses;
- Total estimated healthcare costs associated with the treatment and management of patients;
- Cost-effectiveness of the GEN and E-GEN technology relative to TAU

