##### **2.1.2.2 Evaluate the following for GEN vs E-GEN:**

- Mean percentage change from baseline in HAM-D17 at Week 8
- Percentage of responders in HAM-D17 at Week 8
- Percentage of remitters in HAM-D17 at Week 8

**The treatment groups used for all subsequent analyses (all scales at each time point) will depend on the results in 2.1.2.2**

- If GEN is not statistically different than E-GEN at any endpoint, GEN and E-GEN treatment arms will be combined and compared to TAU
- If E-GEN is statistically superior to GEN at any endpoint, E-GEN will be compared to TAU
- If GEN is statistically superior to E-GEN at any endpoint, GEN will be compared to TAU

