### **2.1.2.3 The subsequent secondary objectives are to evaluate the following for treatment groups determined in 2.1.2.2:**

- Mean percentage change in HAM-D6 (see definition in 7.3) from baseline to Week 8;
- Mean percentage change in the 16-item Quick Inventory of Depression Symptomology (QIDS-SR16) from baseline to Week 8;
- Mean percentage change in the 9-item Patient Health Questionnaire (PHQ-9) from baseline to Week;
- Percentage of responders at Week 8 in each treatment group on the HAM-D6, QIDS-SR16, PHQ-9 (see definition in 7.1);
- Percentage of remitters at Week 8 in each treatment group on the HAM-D6, QIDS-SR16, and PHQ-9(see definition in 7.2)

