## **5 EFFICACY ANALYSIS**

### **5.1 Primary Efficacy Analysis**

The primary measure of efficacy is the percentage change from baseline to week 8 in HAM-D17. The percentage change from baseline in HAM-D17 will be analyzed using a Mixed Model for Repeated Measures (MMRM). The model will include treatment, week (4 & 8), treatment-by-week interaction, baseline HAM-D17 score, baseline HAM-D17-by-week interaction as fixed effects. Unstructured covariance between measurements at weeks four and eight, from the same patient, will be incorporated into the model. If there is a convergence issue, Toeplitz covariance will be used. The MMRM method employed here is known as Maximum Likelihood (ML) to effectively handle the missing values as discussed in Section 3.4. The p-value will be derived from the T-test for comparing two treatment arms at week 8 (treatment by week interaction term). If overwhelming evidence suggests that the normality assumption is not satisfied, complete case analyses (CCA) of the primary efficacy endpoint will be conducted for the PP population for the completers of week eight. The primary endpoint will be analyzed by fitting an analysis of covariance (ANCOVA) model which includes baseline HAMD-17 score. Robust regression method (M Estimation Method by Huber) will be used for CCA to detect potential outliers and appropriately weigh the influence of the outliers should they exist.

As a sensitivity analysis, complete case analyses (CCA) of the primary efficacy endpoint will be conducted for the PP population for the completers of Week 8. The primary endpoint will be analyzed by fitting an analysis of covariance (ANCOVA) model which includes treatment, baseline HAMD-17 score, age, and gender. If age and gender are not statistically significant, they may be dropped from the final model. Robust regression method (M Estimation Method by Huber) will be used for CCA to detect potential outliers and appropriately weigh the influence of the outliers should they exist.

The above MMRM and CCA analyses will also be conducted for the ITT population.

The primary methods for checking the normality assumption will be through graphical assessment using a Q-Q plot and histogram of the residuals. If the points for the Q-Q plot are approximately linear and if the histogram is approximately bell-shaped, the residuals will be considered normally distributed.

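### The SAP specifies no E-GEN versus GEN analysis of weight change, the outcome that E-GEN's added markers target

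*SAP*

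**What the plan says.** Protocol 3.3 and 7.1.2 describe E-GEN as the GEN test plus seven markers for antipsychotic-induced weight gain, with all other procedures the same. Protocol 4.3 sets a secondary objective, "To compare the three intervention alternatives (GEN, E-GEN, and TAU) with respect to" a list of outcomes that contains "Medication side effects, including weight gain". Protocol 8.2.1 (xi) measures this by weight and waist-to-hip ratio but gives no model.

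SAP 1.2 states that the SAP supersedes the protocol's analysis plan. In the SAP:

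- 2.1.2.2 compares GEN with E-GEN on three endpoints only: HAM-D17 percentage change, responders and remitters at Week 8.
- The same section then sets a rule: "The treatment groups used for all subsequent analyses (all scales at each time point) will depend on the results in 2.1.2.2". Its first branch reads "If GEN is not statistically different than E-GEN at any endpoint, GEN and E-GEN treatment arms will be combined and compared to TAU", its second "If E-GEN is statistically superior to GEN at any endpoint, E-GEN will be compared to TAU", and the third is the mirror image for GEN.
- 2.1.4 lists weight gain at Week 8, Week 12 and Month 12 as an exploratory, safety or tolerability objective and names no comparison groups.
- 2.2.3, the matching list of variables, includes UKU and FIBSER but not weight. Waist-to-hip ratio is named nowhere in the SAP.
- 5.3 holds the only weight model: "Continuous measures including UKU, FIBSER, and weight gain may be analyzed in a similar manner as for the primary efficacy variable above".

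**The concern.** E-GEN versus GEN on weight is the contrast most directly tied to what E-GEN adds. Protocol 4.2 makes the utility of the new markers, relative to GEN, a primary objective. A plan that leaves this contrast unspecified could finish without a planned estimate of it.

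Two things are at stake. First, fitting any weight model is discretionary, and unless the 2.1.2.2 rule applies, so is the choice of arms. Both decisions could then be made after the data are seen. Second, if the rule does apply, a depression result decides whether the arms are pooled for weight. Similar HAM-D17 results in GEN and E-GEN say little about whether weight-gain markers changed weight, and a pooled comparison with TAU cannot answer that question.

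**Working it through.** The plan gives no figure for weight to reproduce; the sample size in Protocol 10.0 concerns HAM-D17 only. The main check is therefore textual, followed by a precision calculation.

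**Step 1. Does any reading of the SAP yield an E-GEN versus GEN weight contrast?**

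| Reading | Consequence for weight |
|---|---|
| The 2.1.2.2 rule covers weight | Pooled arms vs TAU, E-GEN vs TAU, or GEN vs TAU. No branch keeps E-GEN vs GEN. |
| The rule does not cover weight | 5.3 applies alone. It names no arms and refers to the primary analysis, where "The p-value will be derived from the T-test for comparing two treatment arms at week 8". The primary hypothesis in 2.1.1 is GEN vs TAU. |

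Which reading is right cannot be settled from the text. The rule speaks of all subsequent analyses, which favours the first. Against that, 2.1.2.3 restates the link ("The subsequent secondary objectives are to evaluate the following for treatment groups determined in 2.1.2.2") and 2.1.3 does likewise, but 2.1.4, where weight sits, does not; body weight is also arguably not one of the scales in the rule's parenthesis. Neither reading specifies the contrast.

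**Step 2. Is the model in 5.1 usable for weight as it stands?** It contains Weeks 4 and 8 only, has baseline HAM-D17 as covariate, and analyses percentage change. The weight objective in 2.1.4 extends to Week 12 and Month 12. Visits, covariate and outcome scale therefore need to be stated.

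**Step 3. What does pooling lose?** With equal arms, the expected pooled difference from TAU is (dE + dG)/2, where dE and dG are the effects in E-GEN and GEN. An effect of 0.8 kg in E-GEN and none in GEN gives (0.8 + 0)/2 = 0.4 kg. An effect of 0.4 kg in both gives (0.4 + 0.4)/2 = 0.4 kg. The pooled result cannot tell these apart.

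**Step 4. How precise would the separate contrast be?**

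- From Protocol 10.0: 190 per arm and 16.7% discontinuation by Week 8, so 190 × (1 − 0.167) = 158.3, about 158 evaluable per arm.
- Assumed, not in the documents: SD of weight change 4-5 kg; a 2 kg difference among antipsychotic users; 10%, 25% or 40% of each arm exposed. Clustering and covariate adjustment are ignored.
- 95% CI half-width = 1.96 × SD × √(2/158) = 0.88 kg (SD 4) to 1.10 kg (SD 5).
- Diluted all-patient differences: 2 × 0.10 = 0.2 kg, 2 × 0.25 = 0.5 kg, 2 × 0.40 = 0.8 kg. All are below the half-width.

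Two-sided power at 0.05, normal approximation, over SD 5 to SD 4. For two arms z = 2f/(SD × √(2/158)), with f the exposed share. For pooled arms against TAU the root becomes √(1/316 + 1/158), and the numerator is f if only E-GEN affects weight or 2f if both arms share the full effect.

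| Exposed | E-GEN vs GEN, effect in E-GEN only | Pooled vs TAU, effect in E-GEN only | Pooled vs TAU, shared effect |
|---|---|---|---|
| 10% | 6.5-7.3% | 5.5-5.8% | 7.0-8.1% |
| 25% | 14.4-19.9% | 8.1-9.8% | 17.7-25.0% |
| 40% | 29.6-42.8% | 13.0-17.7% | 37.5-53.7% |

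Pooling helps the comparison with TAU when both arms share the effect. In that case the true E-GEN versus GEN difference is zero, and the pooled result cannot show it.

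**The case against.** The strongest reply is that much of this is already planned. SAP 4 requires separate TAU, GEN and E-GEN columns in the summary tables, with effect sizes and 95% CIs where appropriate, and 2.1.4 names weight at three time points. Weight is classed as exploratory or safety, and the optional wording in 5.3 also covers adverse-event percentages, UKU and FIBSER. The SAP does compare E-GEN with GEN on HAM-D17, the outcome that Protocol 16.1.3 uses for the second primary objective. The separate weight contrast would also be imprecise: every difference assumed above is smaller than the CI half-width.

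Most of this stands, and it limits the point. A reader might infer that weight will go unreported by arm. The documents do not support that: the data are collected and the table layout can show them. A reader might also infer that the SAP rules out E-GEN versus GEN on weight. That depends on the 2.1.2.2 rule reaching 2.1.4, which is arguable; if it does not, a three-arm model under 5.3 is unnamed but not excluded.

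What the reply does not supply is a commitment. A general table layout with effect sizes at discretion does not promise this estimate. Low precision is a reason to fix the contrast and its interval in advance, not to leave them open.

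**Conclusion.** The point holds, as a gap in planned inference. The protocol promises a three-arm comparison on weight gain; the superseding SAP offers one optional model with no contrast, omits weight from its variable list, and may let a HAM-D17 result pool or drop an arm. This conclusion rests on the text alone and needs none of the numerical assumptions. The HAM-D17 primary analysis is unaffected. The change should be made, but the trial does not stand or fall on it.

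The gain is an interpretable estimate. Nobody should expect a decisive test: under an assumed SD of 4-5 kg and 158 evaluable per arm, the Week 8 half-width is about 0.9-1.1 kg. The documents give no attrition figure beyond Week 8, so later visits are likely less precise. The documents give no SD, exposure or expected effect for weight, and nothing was calculated for waist-to-hip ratio.

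**What to change.** In SAP 5.3, state that change in weight (kg) and in waist-to-hip ratio will be analysed:

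- in the ITT population (SAP 3.2.2), with three separate arms: E-GEN vs GEN, E-GEN vs TAU and GEN vs TAU, regardless of the 2.1.2.2 result;
- with a repeated-measures model using the baseline value of the same measure as covariate and visits at Weeks 4, 8, 12 and Month 12;
- with estimates and 95% CIs reported at Week 8, Week 12 and Month 12, labelled exploratory, and a note that a null is not evidence of no weight effect.

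Add both measures to SAP 2.2.3.

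Cost: no new data, since the schedule in Protocol 9.0 already collects both measures at all these visits. The work is a short model specification plus the list entry. It yields up to 3 contrasts × 2 measures × 3 time points = 18 exploratory estimates, against about 3 for weight alone under the 2.1.2.2 rule, so none should carry a confirmatory claim.
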